| A4.5 | Statistical considerations | 43 |
| A5. | EXPECTED SERIOUS ADVERSE EVENTS..... | 44 |
| A6. | NON-UK SAFETY REPORTING REQUIREMENTS | 45 |
| A7. | LIST OF ABBREVIATIONS | 46 |

CORE TRIAL SUMMARY

[figure not shown]
| | |
|-----------------------|--|
| PROTOCOL TITLE | CORE: A randomised trial of C onventional care versus R adioablation (stereotactic body radiotherapy) for E xtracranial metastases |
| TARGET DISEASE | Breast, prostate and non-small cell lung cancer |
| STUDY OBJECTIVES | 
Primary: To evaluate if the addition of SBRT to standard therapy improves progression free survival outcomes in patients with a limited burden of oligometastatic disease.
 
Secondary:
 
 1. To demonstrate feasibility of recruitment 2. To demonstrate deliverability of SBRT within dosimetric constraints 3. To evaluate if the addition of SBRT to standard therapy improves overall survival 4. To evaluate the lesion local control rates in those receiving SBRT 5. To evaluate the acute and late toxicity associated with the addition of SBRT to standard therapy 6. To compare the quality of life (QoL) in patients receiving SBRT compared to those receiving standard therapy alone. 
Exploratory: To evaluate if the addition of SBRT to standard therapy improves freedom from widespread metastatic disease (FFWMD).
 |
| STUDY DESIGN | Phase II/III, multi-centre, parallel group randomised controlled trial. |
| TRIAL POPULATION | Patients with breast, prostate or non-small cell lung primary cancer and ≤3 extracranial oligometastases suitable for SBRT. |
| RECRUITMENT TARGET | 230 patients |
| TRIAL DESIGN | Patients will be randomised (1:1) between: 
 1. Standard of care (SOC) therapy (Control) 2. Stereotactic Body Radiation Therapy (SBRT) + SOC. SBRT dose and fractionation regimen will be dependent on metastatic site and proximity to normal tissues with SBRT delivery being non-platform specific. |
| PRIMARY ENDPOINT | Progression Free Survival (PFS) |
| SECONDARY ENDPOINTS | 
 1. Feasibility of recruitment 2. Feasibility of SBRT delivery 3. Overall survival (OS) 4. Local lesion control 5. Acute and late toxicity related to SBRT treatment. 6. Patient reported QoL |
| EXPLORATORY ENDPOINTS | Freedom from widespread metastatic disease (FFWMD). |
| ELIGIBILITY CRITERIA | 
Inclusion criteria
 
 1. Age ≥ 18 years 2. WHO performance status 0-2 3. Histological confirmation of primary breast, non-small cell lung (NSCLC) or prostate cancer 4. Predicted life expectancy > 6 months |

| | |
|--|--|
| | 
5. ≤ 3 metastatic lesions (total). A maximum of 2 different organ systems (e.g. liver, lung, bone, nodal) may contain metastases but the total number of lesions must not exceed 3.6. All metastases must be visible, imaging defined targets and be suitable for treatment with SBRT in accordance with the dose fractionation options specified in the protocol.7. Patients who have received prior ablative therapy (e.g. surgery, RFA or SBRT) for metastatic disease are eligible, as long as this site is controlled on imaging at the point of trial entry and the total number of metastases over time since diagnosis of metastatic disease does not exceed 3. Patients with 2 or 3 metastases in which ablative therapy (e.g. surgery/RFA) to 1 site is deemed appropriate as part of standard therapy may be entered into the trial after ablative treatment, following successful delivery of clinical treatment. Ablative therapy (e.g. surgery, RFA, cryoablation, SBRT) is not permissible as a standard of care option following randomisation for patients as part of the trial.8. Metachronous metastatic disease presentation only. Primary site must be controlled. NSCLC patients with synchronous presentation of a single brain metastasis with the primary lung malignancy are eligible as long as both sites of disease have received radical treatment. Both primary lung site and solitary synchronous brain metastasis must be controlled at trial entry, and the total number of metastases over time including the brain metastasis must not exceed 3. Disease-free interval: Breast: ≥ 6 months from completion of radical treatment including any adjuvant therapy to diagnosis of metastases. Patients who have relapsed whilst on adjuvant endocrine therapy are eligible. NSCLC: ≥ 4 months from completion of radical treatment (not including any adjuvant chemotherapy) to diagnosis of metastases. Prostate: ≥ 6 months from completion of radical treatment including any adjuvant therapy to diagnosis of metastases. Patients who have relapsed whilst on adjuvant endocrine therapy are eligible.9. Systemic therapy naïve in the metastatic setting. Prior systemic therapy in the adjuvant setting is permitted. Patients who have had a change in endocrine therapy due to diagnosis of oligometastatic disease can be entered into the CORE trial as long as entry is within 8 weeks of this change in therapy for prostate cancer patients and within 10 weeks of this change in therapy for breast cancer patients.10. Adequate baseline organ function to allow SBRT to all relevant targets11. Negative pregnancy test (for women of childbearing potential)12. Written informed consent |
|--|--|

| | |
|------------------|---|
| | 
Exclusion criteria
 
 1. Intra-cranial metastases (not meeting above inclusion criterion 8) 2. Malignant pleural effusion 3. Malignant peritoneal disease 4. Any single metastasis >6cm,(>5cm for lung metastases) 5. Prior radiotherapy to a site that precludes safe delivery of SBRT. 6. Co-morbidities precluding staging or follow up imaging, or precluding procedures required to facilitate SBRT 7. Loco-regional nodal relapse where surgery is considered the standard of care and is technically feasible. Patients with internal mammary chain or supraclavicular fossa lymph node relapses of breast cancer are eligible if SBRT dose constraints can be met. Patients with axillary nodal relapse from breast cancer are excluded. 8. Spinal cord compression, or impingement of the cord or any other situation whereby the clinician feels that urgent radiotherapy to the spine is required (within 24 hours). 9. Any condition or significant clinical co-morbidities that precludes the safe delivery of SBRT (e.g. history of clinically significant diffuse interstitial lung disease if SBRT to lung metastases or lesions adjacent to lungs are considered or clinically significant colitis i.e. ulcerative colitis /Crohn's disease if SBRT to the pelvis or abdomen is considered). 10. Prostate cancer patients relapsing on Androgen Deprivation Therapy (ADT) which was started for biochemical relapse without staging investigations to define their relapse status, or who have relapsed on CAB which was started for biochemical relapse. 11. Prostate cancer patients receiving or have previously received abiraterone, enzalutamide or chemotherapy e.g. docetaxel. 12. Previous malignancy within the last 2 years (except basal cell carcinoma or squamous cell carcinoma of the skin), or if previous malignancy is expected to significantly compromise 5 year survival. 13. Patients whose entry to the trial will cause unacceptable clinical delays to their planned management. 14. Any psychological, familial, sociological or geographical condition potentially hampering compliance with the study protocol and follow-up schedule. |
| 
FOLLOW UP
 | 
All patients will be reviewed every 3 months with a clinical examination and tumour markers (where applicable) during years 1 and 2, and 6 monthly thereafter up to 5 years. Staging and follow up imaging protocols will be tumour type dependent:
 
 • Breast = 3 monthly CT scans for years 1 & 2, and 6 monthly thereafter to 5 years. • NSCLC = 3 monthly CT scans for years 1 & 2, 6 monthly to year 3 and then annually to year 5. • Prostate = CT will be performed at 6, 12 and 24 months with imaging triggered by appropriate PSA rises. A rising PSA defined as 2 successive PSA rises from nadir, measured a minimum of 4 weeks apart. If the overall PSA rise has a doubling time of ≥ 3 months or |

| | |
|--|---|
| | 
the PSA level has doubled the original PSA value at trial entry or if clinically indicated, then restaging should be considered.
 
All patients will have a toxicity assessment at each clinic visit and patient reported quality of life (QOL) assessment at 3, 6, 12, 18 & 24 months.
 |
|--|---|

TRIAL SCHEMA

1 INTRODUCTION

1.1 Background

The term oligometastases was first coined by Hellman and Weischelbaum in 1995 [1]. It describes the concept of an intermediary metastatic state, in which cancer exists as a limited number of metastases at first, before cells acquire the ability to metastasise more widely. It is hypothesized that successful eradication of disease at an oligometastatic stage may improve survival outcomes, and potentially may even result in cure for a select few [2, 3]. Whilst it is difficult to quantify the exact number of patients with true oligometastatic disease, an increase in the use of surveillance imaging, together with improved diagnostic sensitivity, has led to more patients being diagnosed with a limited metastatic disease burden at an asymptomatic stage.

Historically once a solid tumour has acquired the ability to spread to distant sites, treatment has focused on systemic therapy given with palliative intent. However it is now established that long term survival is possible following surgical resection of limited sites of metastatic disease. In a series of mixed primary sites, 26% of patients remained alive 10 years after pulmonary metastectomy [4]. Similarly, 5-year survival rates following chemotherapy and surgery for liver metastases in colorectal cancer have now improved to 40-50% [5-7]. This supports the concept that an oligometastatic disease state exists where radical treatment may result in long-term survival.

Stereotactic body radiation therapy (SBRT) is an advanced radiotherapy technique that may be used to deliver ablative doses of radiotherapy. It is non-invasive and can be used to treat a variety of oligometastatic disease sites. It may also be considered in patients when the option for surgery is not possible.

1.2 Known risks and benefits of SBRT

A number of retrospective and prospective cohort studies reporting outcomes for SBRT for the treatment of oligometastatic disease sites have been reported. These data have recently been succinctly reviewed [2, 3]. In general these studies demonstrate high rates of local control, together with acceptable rates of toxicity (generally $<10\% \geq$ Grade 3). Anecdotally progression-free survival rates in these cohorts are better than would be expected in stage IV disease, with disease-free survival varying from 20-50% at 17-48 months follow up [3]. However survival data from historical cohort studies may be inherently biased as result of a highly selected patient population and other confounders. The lack of randomized data limits interpretation and a control group is required to evaluate the true benefit of adding local therapy to systemic treatment in this context.

Ascertaining which patients are most likely to benefit from such an approach is key. In this trial, only patients with ≤ 3 metastases will be included. This is based on the observations of Salama et al who reported outcomes of 61 patients with 1 to 5 metastases from miscellaneous primary sites treated with SBRT [12]. They found that patients with ≤ 3 metastases have better progression free and overall survival when compared to patients treated for 4 to 5 metastases, all of whom had experienced progression within 9 months of treatment. In addition 75% of patients with 4 or 5 metastases went on to develop widespread metastatic disease in comparison to 46% of patients with 1-3 metastases.

The potential therapeutic benefit of adding tumour ablation to standard therapy may vary between tumour sites, reflecting both different underlying tumour biology and natural disease courses. Milano et al reported a series of 121 patients with up to 5 sites of metastases from miscellaneous primary sites with a median follow up of 4.5 years. They found that patients with

breast cancer had significantly improved local control and overall survival rates at 6 years (LC 87%, OS 47%), in comparison to non-breast patients (LC 65%, OS 59%) [9]. Additionally, patients with breast cancer were less likely to develop widespread metastatic disease following SBRT compared to those with non-breast cancers (36% vs 13%). These results may simply reflect the better overall prognosis of patients with metastases from breast cancer. At present there is insufficient evidence to be able to predict which cancers may benefit most from such an approach. In this trial we will investigate the scientific hypothesis that the addition of SBRT to standard therapy improves survival outcomes, focusing on common primary tumour sites where oligometastatic disease is encountered.

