11.1.2 Sample size

This phase II screening study has been designed with a primary endpoint of PFS, and relaxed one-sided $\alpha=0.20$ and $\beta=0.20$ (13). The control arm PFS is estimated based on the expected contribution of each primary tumour site to the overall final sample size. Based on observed recruitment in the first year this is estimated at 75% prostate, 14% breast and 11% lung. Assuming a median PFS of 5 months for NSCLC, 12 months for breast and 18 months for prostate patients (14-22), it is estimated that the median PFS in the control group after randomisation will be 16 months. The phase II SABR-COMET trial targets a hazard ratio (HR) for OS of 0.6 (23). For CORE, a more conservative effect size has been chosen reflecting clinical opinion of what would constitute a PFS signal worthy of a phase III OS trial. In order to detect a HR of 0.75 for improvement of PFS i.e. extending the median cohort PFS by 4 months in the experimental arm with 80% power, a total of 230 patients are required (138 events). Assuming a 5% rate of patients lost to follow up at the point of data analysis, a total of 242 patients will be required (121 per treatment group). Dependent on observed rates of accrual this total may increase to a maximum of 270 to allow for each cohort to achieve a minimum of 50 patients. The sample size calculations, made using the *artsurv* command in Stata version 13, assume 50% recruited in both years 1 and 2 and 12 months of additional follow up.

The decision rule to proceed to phase III will be based on a 3 outcome design. An overall result significant at the 10% level would support continuation to phase III; significance between 10% and 20% would require supportive evidence from secondary endpoints with a particular emphasis on local tumour control and FFWMD. If the significance is >20% then the study will not progress to phase III unless there is clear

heterogeneity of outcomes between the 3 tumour subgroups supporting a signal in selected tumour sites in which case consideration would be given to progressing to an extended phase 2 evaluation for that tumour site alone.

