11.1.3 Treatment allocation

Patients will be randomised between SOC and SBRT + SOC in a 1:1 ratio. Patients will be randomised at different stages of their disease depending on the primary tumour site and in accordance with the inclusion and exclusion criteria. Treatment allocation will use minimisation with balancing factors of primary tumour site (breast, NSCLC, prostate) and centre. In tumour sites where there is felt to be a further important prognostic variable which may affect the primary PFS endpoint, a further stratification will be performed, as outlined below, to ensure the 2 treatment groups are balanced.

- **Breast:** patients will be stratified additionally into ER+ (relapsed post adjuvant therapy) vs all other subgroups, to reflect the difference in median PFS. It is acknowledged that breast cancer is a heterogeneous disease, essentially composed of several sub-groups with varying prognosis, dependent on receptor status, disease free interval (DFI) and prior adjuvant therapy. Whilst there is an argument in terms of homogeneity for limiting the eligible patient population to 1 sub-group only, such as ER+ disease, we feel it is more pragmatic at this stage to include all comers. The likely frequency of eligible patients within each sub-group is largely unknown and to ensure feasibility of recruitment, restricting trial entry to a particular sub-group from the outset is not warranted.
- **NSCLC:** stratified additionally into EGFR+ versus the remainder (with a similar rationale to the breast group).
- **Prostate:** patients will be stratified additionally into 2 groups:
 - 1) Patients who are endocrine therapy naïve
 - 2) Patients who are castrate resistant.

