11.2.3 Exploratory endpoint

Freedom from widespread metastatic disease (FFWMD) will be measured from the time of randomisation until radiological evidence of disease progression, which is not suitable for radical salvage therapy (e.g. surgery, RFA or SBRT). Widespread metastatic disease is defined as greater than or equal to 4 metastatic sites, regional or distant, or a combination thereof. This will reflect the trial entry criteria, i.e. eligible patients must have ≤ 3 sites of metastatic disease relapse, all technically suitable for salvage therapy.

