11.2.4 Statistical analysis plan

Analyses will be according to the intention-to-treat method. Time to event endpoints will be presented using Kaplan Meier methods with treatment effects presented as relative and absolute estimates. Hazard ratios will be derived from Cox proportional hazards models stratified by disease site. The time point of interest is 1 year from randomisation. The log rank test will be used to compare treatment groups stratified by disease site. For PFS, patients who are event free at time of analysis will be censored using the date of last disease assessment (imaging for breast, NSCLC and PSA assessment for prostate). An appropriate alternative method will be used if there is evidence of non-proportional hazards.

Acute and late toxicity will be summarised as frequencies and percentage at each time point. Non-haematological grade 2 or greater (G2+) toxicities related to SBRT treatment are of primary interest. The proportion experiencing G2+ will be presented by treatment group and comparisons made between treatments using Fishers exact tests, separate comparisons will be made of acute and late toxicity.

Quality of life data will be analysed using standard algorithms to derive scores and handle missing data according to the EORTC scoring manual. Descriptive statistics (median, IQR, range) will be presented by treatment group at each time-point. Statistical comparisons will be made at 12 and 18 months. Analyses to account for the longitudinal nature of the data may also be used.

A planned exploratory analysis will be performed to investigate the treatment effect in each primary site subgroup. This will be summarised with a hazard ratio and compared in each subgroup to look for consistency of effect (accepting that there will be little power for a formal test of heterogeneity). There will be very limited power and much uncertainty about these estimates, and therefore they will be interpreted with caution.

Further details of analysis methods will be specified in a Statistical Analysis Plan in accordance with ICR-CTSU Standard Operating Procedures.

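### The number of metastases at entry is partly built into the FFWMD endpoint, yet it is neither balanced at allocation nor included in the stated FFWMD analysis

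*Protocol*

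**What the plan says.** - **Background.** Protocol 1.2 reports from a cited series that "75% of patients with 4 or 5 metastases went on to develop widespread metastatic disease in comparison to 46% of patients with 1-3 metastases".
- **Entry.** Protocol 5.3, criteria 5 and 7, allows up to three metastases. Lesions ablated earlier in the metastatic course count towards the three.
- **Endpoint.** Protocol 11.2.3 states: "Widespread metastatic disease is defined as greater than or equal to 4 metastatic sites, regional or distant". Section 8.4 joins that threshold by an and/or to progression that local treatment can no longer salvage. Section 4.3 describes only loss of amenability to ablation and gives no count.
- **Allocation.** Protocol 11.1.3: "Treatment allocation will use minimisation with balancing factors of primary tumour site (breast, NSCLC, prostate) and centre", plus one further factor inside each tumour site (ER, EGFR or castration status). Number of metastases is not among them.
- **Analysis.** Protocol 11.2.4: "Hazard ratios will be derived from Cox proportional hazards models stratified by disease site". The log-rank test has the same strata. More detail is deferred to a SAP.
- **Use.** FFWMD is labelled exploratory in 4.3 and 11.2.3, yet in the decision rule of 11.1.2 "significance between 10% and 20% would require supportive evidence from secondary endpoints with a particular emphasis on local tumour control and FFWMD".

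**The concern.** By the count route, and if lesions are counted cumulatively, a patient entering with three metastases is one new site from the event and a patient entering with one is three away. That is stronger than ordinary prognostic value, because the baseline value fixes part of the distance to the endpoint. Allocation leaves this variable to chance and the stated model ignores it.

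At stake is the reading of FFWMD when PFS lands in the middle zone. Of the two endpoints emphasised there, local control is framed in objective 5 of section 2.2 as a rate among those receiving SBRT. FFWMD is therefore the one clearly set up as a comparison between arms. If one arm happens to hold more three-lesion patients, its FFWMD result shifts for a reason unrelated to treatment, and an adjustment proposed only then would look post hoc.

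**Working it through.** **1. The plan's own figure.** Section 11.1.2 uses one-sided alpha 0.20 and power 80%: "In order to detect a HR of 0.75 for improvement of PFS". Schoenfeld's formula gives d = 4(0.8416 + 0.8416)² / (ln 0.75)² = 4 × 2.833 / 0.08276 = 137 events; Freedman's gives 139. The plan states 138, for which power is 80.2%. For the control arm, "it is estimated that the median PFS in the control group after randomisation will be 16 months"; the other median is 16/0.75 = 21.3 months. With exponential PFS, 24 months' uniform accrual and 12 further months, the mean event probability is 0.580, and 137/0.580 = 236, within 3% of the stated 230. Then 230/0.95 = 242. The PFS calculation reproduces and is not affected by this point. The protocol gives no design figure for FFWMD.

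**2. Assumptions for FFWMD (none is in the protocol).** Entry mixes for 1/2/3 metastases: 70/20/10, 55/30/15 and 33/33/33%. New lesions arise as a Poisson process at 0.04 or 0.08 per month and count cumulatively. Unsalvageable progression arises at 0, 0.01 or 0.03 per month. N = 230, 1:1 simple randomisation, follow-up uniform on 12 to 36 months, no differences between disease sites. The event is the (4 − k)th new lesion, k being the entry count, or unsalvageable progression if earlier.

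**3. Ordinary chance imbalance.** With 115 per arm, the SD of the difference in the share entering with three is √(2p(1−p)/115): 4.0, 4.7 and 6.2 percentage points for p = 0.10, 0.15 and 0.33. The SD of the difference in mean count is √(2·Var(k)/115). With Var(k) = 0.44, 0.54 and 0.67 this is 0.09, 0.10 and 0.11 lesions.

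**4. Effect on the unadjusted HR.** There were 4000 simulated trials per scenario with no treatment effect, regressing the estimated log HR on the difference in mean count. Power used 3000 trials per scenario with all rates multiplied by 0.75 and one-sided 20% tests, unstratified against stratified by k. Ranges run over the three mixes.

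| New lesions per month | Unsalvageable per month | Event by analysis, entry 1 vs 3 | HR factor at 1 SD | HR factor at 2 SD | Power change, points |
|---|---|---|---|---|---|
| 0.04 | 0 | 8% vs 60% | 1.12–1.15 | 1.26–1.32 | +3.7 to +3.8 |
| 0.08 | 0 | 30–31% vs 83% | 1.09 | 1.18–1.20 | +2.4 to +4.8 |
| 0.04 | 0.01 | 27% vs 68% | 1.06–1.08 | 1.13–1.16 | +0.7 to +3.8 |
| 0.04 | 0.03 | 54% vs 79% | 1.03–1.04 | 1.06–1.09 | −0.1 to +0.8 |

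Hand check of the 60%: 1 − (e^(−0.48) − e^(−1.44))/(0.04 × 24) = 1 − (0.619 − 0.237)/0.96 = 0.60.

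On the scale of the estimate's own noise, for the 55/30/15 mix: in the first row the 1-SD shift is 0.138 × 0.94 = 0.13 on the log scale against an SD of 0.287, or 0.45 of an SD. In the last row it is 0.033 × 0.98 = 0.032 against 0.168, or 0.19.

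**5. Error rates with no effect.** The overall chance of one-sided p < 0.20 is 0.19–0.21 with or without stratification by k. Conditional on the imbalance it is:

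| Imbalance in mean count | Unstratified | Stratified by k |
|---|---|---|
| SBRT arm more than 1 SD higher | 0.03–0.13 | 0.18–0.22 |
| SBRT arm more than 1 SD lower | 0.26–0.45 | 0.18–0.24 |

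**6. How often the zone is reached.** Taking the levels as one-sided, PFS falls between 10% and 20% in 10% of trials with no effect. At HR 0.75 the expected Z is 0.2877 × √138 / 2 = 1.690, so the probability is Φ(1.690 − 0.842) − Φ(1.690 − 1.282) = 0.802 − 0.658 = 0.14.

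**The case against.** The strongest reply is that nothing here is an error. Randomisation covers chance imbalance on average, overall type I error is intact, and covariates for an exploratory endpoint are usual SAP material. The first two parts stand. The third stands only in part: 11.2.4 does not leave the model open but names one, with disease site as the only stratum. The SAP may already add entry count; if so, only the protocol text needs aligning.

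Other parts of the reply also stand and limit the point:

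- A reader might infer that FFWMD is reached only at four lesions. Sections 4.3, 8.4 and 11.2.3 do not support that: unsalvageable progression qualifies at any count, and the effect shrinks as that route grows.
- The protocol counts sites and does not say whether ablated lesions stay in the total, so the distances of one, two and three are an assumption.
- A reader might take the comparison in section 1.2 as proof of a gradient. It sets four or five metastases against one to three, in a series of 61 patients, and says nothing about differences within the eligible range.
- FFWMD supports the decision rather than making it. PFS sets the zone, local control is emphasised too, and no FFWMD cut-off is stated.
- Section 7 records sites of disease, not explicitly a number, and Appendix A1.2 lets several non-target lesions in one organ be entered as one item. The count must nevertheless be known to confirm eligibility.

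**Conclusion.** The point holds as a matter of conditional error and lost precision in one supportive comparison. An imbalance of ordinary size moves the unadjusted FFWMD HR by about 3% to 15% per SD: towards the upper end if the count is the main route to the event, towards the lower end if unsalvageable progression dominates. Adjustment gains about 0 to 5 points of power. All of these sizes rest on the assumed entry mixes, lesion rates and cumulative counting in the working. The structural facts (fixed threshold, entry at one to three, count absent from allocation and analysis) come from the protocol itself.

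Two stronger readings are not supported. It is not systematic bias or inflated type I error, because the overall rate stays near 0.20. Nor is it a case for changing the primary PFS model: the PFS definition contains no count threshold, and no calculation here shows a gain for PFS.

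**What to change.** In 11.2.4, keep the disease-site strata and prespecify the number of metastases at randomisation (1, 2 or 3, counted as for eligibility) as a stratum or covariate in the FFWMD analysis. In 11.1.2, name that adjusted HR as the FFWMD evidence for the 10–20% zone. Report the distribution of entry count by arm. Show the unadjusted HR beside it, since the two need not coincide even in balanced arms: with rates multiplied by 0.75, the 55/30/15 mix, 0.04 new lesions per month and the count route only, they averaged 0.68 unadjusted and 0.65 stratified.

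Leave the primary PFS analysis unchanged; adjustment for count there is at most a sensitivity analysis. The allocation scheme need not change.

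The cost is a few lines of text and, if the eligibility checklist does not already hold the count as a number, one data field completed from information already needed for eligibility. Sample size and patient procedures are untouched. The wording should be settled before outcome data by arm are seen.
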